#### 6.2.4.1 Medical History

General medical history will be coded using the Medical Dictionary for Regulatory Activities (MedDRA) Version 25.0 and summarized by body system organ class (SOC) and preferred term (PT) for each treatment group and overall.

A subject data listing of medical history will be provided, including SOC and PT, current medical condition, date of diagnosis or surgical procedure or onset of symptoms, and end date/ongoing.

### 6.2.5 Prior and Concomitant Therapy

All investigator terms for medications recorded on the CRF will be coded using the World Health Organization Drug Dictionary (WHO DD) Version of March 2022.

Prior medications will be defined as the medications that were started prior to the first dose of study drug. Concomitant medications will be defined as the medications that (i) started before the first dose of study drug and were continuing at the time of the first dose of study drug, or (ii) started on or after the date of the first dose of study drug up to 30 days after the subject's last dose. Medications that cannot be determined to be prior/concomitant due to missing or incomplete dates will be regarded as concomitant.

Prior medications will be summarized by anatomical class (Anatomical Therapeutic Chemical [ATC] Level 1), pharmacologic class (ATC Level 3), and WHO DD preferred term. A similar summary will also be provided for concomitant medications except antidiarrheal therapy and antihypertensive therapy. Concomitant antidiarrheal therapy and antihypertensive therapy will be summarized separately.

Prior anticancer therapies including anticancer medications, anticancer procedures and anthracycline therapy will be summarized and listed.

Prior and concomitant medications/therapies will be summarized for the Full Analysis Set.

### 6.2.6 Treatment Compliance

Records of treatment compliance for each subject will be kept during the study, including the Follow-up Period. Clinical research associates will review treatment compliance during investigational site visits and at the completion of the study. Received dose as percent of planned dose per subject (ie, relative dose intensity) will be summarized as described in [Section 6.6.1.2](#); no other analysis of treatment compliance is planned.

## 6.3 Data Analysis General Considerations

### 6.3.1 Pooling of Centers

Subject data from all centers will be pooled for all analyses. Center will not be considered as a factor in the analyses.

### 6.3.2 Adjustments for Covariates

The stratified log-rank test for the primary efficacy endpoint, PFS as assessed by IIR, the secondary efficacy endpoint, OS, the stratified Miettinen and Nurminen's method for the secondary efficacy endpoint of ORR, and the stratified Cox regression analyses to estimate

hazard ratios (time-to-event efficacy endpoints) will be performed using the following randomization stratification factors from IRT.

- Time to first relapse/refractory disease (early [ $<18$  months] or late [ $\geq 18$  months])
- Age ( $<18$  and  $\geq 18$  years)

In case of low numbers of subjects enrolled within any combination of stratification factors, subjects from the low enrollment combination(s) of the stratification factors may be pooled for analysis.

Based on a blinded review of the data, the number of subjects in the level of the stratum “time to first relapse/refractory disease  $\geq 18$  months” is approximately 11 subjects out of 81 subjects in the ITT population. To ensure a sufficient number of participants in each stratum within each treatment arm, “time to first relapse/refractory disease” has been removed as a stratification factor in the analyses. Thus, only the stratification factor “age at randomization” will be included in any stratified analyses.

Other demographic and baseline variables may be included and adjusted in the statistical models as sensitivity analyses if deemed necessary.

### 6.3.3 Multiple Comparisons/Multiplicity

No multiplicity adjustment will be made for this study.

### 6.3.4 Examination of Subgroups

For the primary efficacy endpoint PFS as assessed by IIR, the median PFS, hazard ratio, and corresponding 95% confidence intervals may be generated for the following subgroups, as appropriate.

- Age ( $<18$  years,  $\geq 18$  years)
- Time to first relapse ( $<18$  months,  $\geq 18$  months)
- Sites of metastasis [Lung only, Others (+/- lung)]
- Prior Ifosfamide +/- Etoposide (Yes, No)
- Measurable disease [Yes (Subjects with at least 1 target lesion), No (Subjects with only non-target lesions)]

For the safety endpoints, the following TEAE tables will be provided by age group (years) category ( $<18$  years,  $\geq 18$  years) and gender.

- Overall summary of TEAE
- TEAEs in decreasing frequency of PT
- Serious TEAEs in decreasing frequency of PT

Other exploratory subgroup analyses may be conducted if appropriate.

### 6.3.5 Handling of Missing Data, Dropouts, and Outliers

For efficacy endpoints related to ORR, which summarize the percentage of responders, missing responses will not be imputed.

For incomplete dates involving efficacy and safety data such as adverse events (see below), concomitant medications, laboratory assessments, vital signs, and ECG data, a conservative imputation will be used for calculation if needed. The imputation rules will be specified in study analysis dataset specifications with more details.

Adverse events with incomplete dates will be considered treatment emergent if:

- Day and month are missing and the year is equal to or after the year of the first study drug dose date
- Day is missing, and the year is after the year of the first study drug dose
- Day is missing and the year is equal to the year of the first study drug dose date and the month is equal to or after the month of the first dose date
- Year is missing; or complete date is missing

HRQoL analysis will follow the FDA and the European Medicines Agency (EMA) PRO guidelines. Handling of missing values for HRQoL analyses will be detailed in a separate SAP and HRQoL report.

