## **6.6 Safety Analyses**

All safety analyses will be performed on the Safety Analysis Set. Safety data, presented by treatment group, will be summarized on an “as treated” basis using descriptive statistics (eg, n, mean, standard deviation, median, minimum, maximum, Q1, and Q3 for continuous variables; n [%] for categorical variables), as appropriate. All safety data will be summarized up to the last dose + 30 days or the data cutoff date, whichever occurs earlier. Optional lenvatinib crossover treatment is permitted by protocol. For subjects in Arm B who crossed over to optional treatment with lenvatinib alone or lenvatinib plus chemotherapy, data records occurring on or after the date of the crossover (date of first administration of lenvatinib) will be excluded from this analysis. In addition, for these subjects, data occurring on or after the date of the crossover will be summarized and listed separately for selected parameters as appropriate.

Safety variables include TEAEs, clinical laboratory parameters, vital signs, 12-lead ECG results, Lansky play scores or Karnofsky performance scores, physical examination, height, tooth formation abnormalities, closure of proximal tibial plates, Tanner Stage, and left ventricular ejection fraction (LVEF). Study Day 1 for all safety analyses will be defined as the date of the first dose of study drug.

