#### 6.6.2 Adverse Events

Adverse events will be graded according to the National Cancer Institute [Common Terminology Criteria for Adverse Events \(NCI-CTCAE\)](#), Version 5.0. The AE verbatim descriptions (investigator terms from the CRF) will be classified into standardized medical terminology using the MedDRA Version 25.0. Adverse events will be coded to the MedDRA lower level term (LLT) closest to the verbatim term. The linked MedDRA PT and primary SOC are also captured in the database.

A TEAE is defined as an AE that emerges during treatment (and within 30 days of the last study treatment), having been absent at pretreatment (Baseline) or

- Re-emerges during treatment, having been present at pretreatment (Baseline) but stopped before treatment,  
or  
Worsens in severity during treatment relative to the pretreatment state when the AE is continuous.

Only those AEs that are treatment-emergent will be included in summary tables by treatment group. Exposure-adjusted analyses will be presented for selected AE summaries. For subjects in Arm B who received optional lenvatinib only or lenvatinib plus chemotherapy, adverse events occurring on or after the date of the crossover will be summarized separately by PT in order of decreasing frequency. All AEs, treatment-emergent or otherwise, will be presented in subject data listings.

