### 9.3 Imputation of Missing Data

Unless specified otherwise, no data imputation will be applied for missing safety and efficacy evaluations. For analysis and reporting purposes, partial dates for adverse events, prior and concomitant therapies, disease diagnosis date, and start date of new anticancer therapy will be imputed if needed. Partial dates for laboratory values, vital signs, and ECGs will not be imputed.

The imputation rules will be specified in study analysis dataset specifications with more details.

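### SAP Section 6.3.5 labels AEs treatment-emergent even when their recorded end date precedes the first dose, and contradicts Section 9.3 on imputing partial laboratory, vital-sign and ECG dates

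*SAP*

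**What the plan says.** **Adverse events.** SAP Section 6.3.5 gives four conditions under which an AE with an incomplete date counts as treatment-emergent:

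1. Only the year is known: "Day and month are missing and the year is equal to or after the year of the first study drug dose date".
2. The day is missing and the year is later: "Day is missing, and the year is after the year of the first study drug dose".
3. The day is missing and the year is the same: "the month is equal to or after the month of the first dose date".
4. No usable year: "Year is missing; or complete date is missing".

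Section 6.6.2 defines a TEAE as an AE that "emerges during treatment (and within 30 days of the last study treatment") and was absent at baseline. It adds events that re-emerge during treatment after stopping beforehand, and continuous events that worsen during treatment.

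**Laboratory, vital-sign and ECG dates.** Section 6.3.5 includes them in its general sentence on incomplete dates: "laboratory assessments, vital signs, and ECG data, a conservative imputation will be used for calculation if needed". Section 9.3 says: "Partial dates for laboratory values, vital signs, and ECGs will not be imputed". Both sections leave further detail to the analysis dataset specifications.

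**The concern.** The usual reason for treating a doubtful AE as treatment-emergent is that the available dates cannot exclude it. That reason fails when the record carries an end date before the first dose: nothing is in doubt, yet the rules as written still put the event into the TEAE tables. Pre-treatment events would then be reported as arising on treatment.

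The second problem is plainer. A programmer given a laboratory value with a missing day finds one section that allows imputation and another that forbids it. The choice can matter, because Section 6.6.3 defines on-treatment laboratory tests by date and Section 9.1 picks by-visit values by their distance from the target day. With the conflict unresolved, the treatment of such values would be settled during programming, in an open-label trial, rather than in the plan.

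**Working it through.** The SAP gives no figure on this point, so there is none to reproduce. The check applies the AE rules to example dates and sets the two imputation statements side by side.

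**AE rules.** Assume a first dose on 20 June 2021. The dates are illustrative.

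| Recorded onset | Recorded end | Rule that applies | Result under 6.3.5 | Under 6.6.2 |
|---|---|---|---|---|
| June 2021, day missing | 10 June 2021 | 3: month 6 ≥ 6, same year | Treatment-emergent | Ended before first dose: not a TEAE |
| 2021, day and month missing | 1 March 2021 | 1: 2021 ≥ 2021 | Treatment-emergent | Ended before first dose: not a TEAE |
| Wholly missing | 1 May 2021 | 4: no condition | Treatment-emergent | Ended before first dose: not a TEAE |

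The other two branches of the definition do not rescue these records. An event that has ended cannot worsen during treatment, and a re-emergence would be a new episode with its own dates. Rule 2 raises no such problem when the recorded dates are coherent: an onset in a later year than the first dose cannot have ended before it.

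**Reach of rules 1 and 3 among pre-dose events.** Assume true onset uniform over the 28 days before first dose (28 days being the maximum length of the Prerandomization Phase in Section 4.2.1), with first-dose dates spread evenly over a 365-day year.

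- *Day missing.* For a first dose on day D of the month, the share caught is min(D − 1, 28)/28. Summing min(D − 1, 28) gives 462 for a 31-day month, 434 for a 30-day month and 378 for February. The year total is 7 × 462 + 4 × 434 + 378 = 5,348. Divided by 365 × 28 = 10,220, this is 52%.
- *Day and month missing.* Only first doses in the first 28 days of the year let any onset fall in the previous year. The total is 337 × 28 + (0 + 1 + … + 27) = 9,436 + 378 = 9,814. Divided by 10,220, this is 96%.

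These are shares of pre-dose AEs that already have a partial onset date, before any end-date check. They show that the rules do not screen out such events by themselves. They are not the share of this trial's AEs that would be mislabelled.

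**Imputation of dates.**

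| Data | Section 6.3.5 | Section 9.3 |
|---|---|---|
| Adverse events, concomitant medications | Imputed if needed | Imputed if needed |
| Laboratory, vital signs, ECG | Imputed if needed | Not imputed |

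The sections agree on AEs and concomitant medications and conflict only on the last row. Both are current text. The qualifier in Section 6.3.5 does not reconcile them, because Section 9.3 allows no case in which these dates are imputed.

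**The case against.** The strongest defence of the AE rules is that over-inclusion is an accepted conservative convention, applies identically to both arms, and may be refined in the dataset specifications. Much of this stands: the direction of the convention is reasonable and no between-arm bias follows from it. It does not answer the end-date case, where the record itself settles the question. The specifications are promised as further detail, which does not clearly license overriding four stated rules. For the date conflict, deferral does not help, since both sections defer to the same place with opposite instructions.

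Three stronger readings are tempting, and the SAP does not support them.

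- *That the rules ignore the 30-day limit.* Taken alone they do, but Section 6.6 caps all safety summaries at last dose plus 30 days or data cutoff, Section 6.6.2 puts the limit in the TEAE definition, and Section 4.2.2.2 captures AEs only for 30 days after the last dose.
- *That lenvatinib-period AEs of crossover subjects are systematically booked to Arm B.* Section 6.3.5 decides only whether an AE is treatment-emergent. Its table is decided by Sections 6.6 and 6.6.2, which remove "data records occurring on or after the date of the crossover" from the main analysis and summarize crossover AEs separately. No default is stated for an AE whose partial date is ambiguous around crossover, so the direction is undetermined. The missing default is a minor note.
- *That partially dated laboratory or ECG values are lost under Section 9.3.* That section says the date is not imputed, not that the record is dropped, and Section 9.1 includes all postbaseline assessments in worst-grade and shift tables. The on-treatment window in Section 6.6.3 might exclude some values, but that is an inference.

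**Conclusion.** Two errors stand, both minor. The AE rules in Section 6.3.5 produce a label that contradicts Section 6.6.2 whenever onset is partial, the rule's condition is met, and the end date falls before the first dose. Sections 6.3.5 and 9.3 give incompatible instructions on laboratory, vital-sign and ECG dates. The second is the firmer of the two, because it needs no example to demonstrate.

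The effect is confined to safety records with partial dates. Their number cannot be derived from the SAP; that it is small is a judgement. The AE error over-counts TEAEs in either arm, with no between-arm direction shown. The PFS analysis is unaffected. The conclusion on AEs assumes that end dates are recorded at least in part for some of these events, and that the dataset specifications, which are not at hand, do not already contain an end-date check.

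**What to change.** 1. In Section 6.3.5, add to the AE rules: *unless the AE end date, or its known part, shows that the AE ended before the first dose of study drug*. An end month equal to the month of first dose, with the day missing, does not show this, so such an AE stays treatment-emergent and the conservative convention is kept.
2. In Section 6.3.5, delete laboratory, vital-sign and ECG data from the imputation sentence, so that Section 9.3 governs.
3. State that a partially dated laboratory, vital-sign or ECG value whose known month and year lie within the on-treatment period stays in the worst-grade and shift tables but is left out of by-visit summaries, which need a distance to the target day. Say also how a month that only partly overlaps the period is handled.

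The cost is a few sentences of SAP text and a small change to the derivations, with no new data. The sponsor may also wish to state where an Arm B AE goes when its partial date is ambiguous around crossover. No particular default is recommended: sending every AE compatible with the crossover period to the crossover table would move chemotherapy-period events out of the control arm in one direction only.

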## 6.4 Efficacy Analyses

Efficacy analyses will be based primarily on the Full Analysis Set. The per protocol analysis set will be the secondary analysis set for efficacy endpoints. All tumor assessment analyses using the IIR assessments will be considered primary; all tumor assessment analyses using investigator assessments will be considered supportive analyses. The randomization strata based on IRT will be used in the analyses unless otherwise specified.

All primary statistical analyses will be conducted at the data cutoff date for the analysis of the primary efficacy endpoint, PFS by IIR (ie, when approximately 38 PFS events, as determined by IIR, are observed). Additional analyses will be based on the date of data cutoff for the additional follow-up analysis of OS or at the time of the last subject last visit, whichever occurs later.

### 6.4.1 Primary Efficacy Analysis

The primary efficacy endpoint of PFS per IIR will be analyzed and compared between the 2 treatment arms by the stratified log-rank test adjusted for the randomization stratification factor (refer to [Section 6.3.2](#)). Median PFS will be calculated using the K-M product-limit estimates for each treatment arm along with 2-sided 95% CIs (estimated with a generalized Brookmeyer and Crowley method [[Brookmeyer and Crowley, 1982](#)]). The K-M estimates of PFS will be plotted over time. The stratified Cox regression model will be used to estimate the hazard ratio and its 95% CI.

The PFS by IIR is defined as the time from the date of randomization to the date of first documentation of disease progression based on IIR assessments using RECIST 1.1 or date of death, whichever occurs first.

Determination of the date of PFS event or censoring is summarized in Table 2 below. The table is based on the FDA clinical trial endpoints guidance of 2007 (FDA, 2007). In this study, removal of baseline lesion(s) is permitted after completion of the Week 18 tumor assessment, and palliative radiotherapy of non-target lesions is allowed (see protocol 9.4.7.3). For the primary efficacy endpoint analysis, PFS will be censored according to censoring rules in Table 2. In this analysis, assessments after removal of baseline lesion(s) (considered as a new anticancer therapy) before or after Week 18 will be censored.

**Table 2 PFS Event and Primary Censoring Rules**

| No. | Situation   | Date of Progression or Censoring   | Outcome   |
|-----|---|--|-----------|
| 1   | No baseline or post-baseline adequate tumor assessments*  | Date of randomization  | Censored  |
| 2   | Progression documented between scheduled visits, on or prior to new anticancer therapy                              | Date of first radiologic PD assessment   | PFS Event |
| 3   | No progression at the time of data cutoff   | Date of last adequate radiologic assessment on or prior to data cutoff                         | Censored  |
| 4   | New anticancer therapy started +   | Date of last adequate radiologic assessment on or prior to the start of new anticancer therapy | Censored  |
| 5   | Death without disease progression or any new anticancer therapy   | Date of death  | PFS Event |
| 6   | Death between adequate assessment* (Death before next scheduled assessment or after exactly one missing assessment) | Date of death  | PFS Event |
| 7   | Death or progression after more than one consecutive missed visit/tumor assessment**                                | Date of last adequate radiologic assessment before missed tumor assessments                    | Censored  |

Note:

+ Assessments after removal of baseline lesion(s) (eg, surgical, radiofrequency ablation, cryotherapy, thermoablation, stereotactic radiotherapy, etc.) before or after Week 18 will be censored. Palliative radiotherapy of nontarget lesions is permitted per protocol and will not be considered as a new anticancer therapy.

\* Adequate tumor assessment is radiologic assessment at regular intervals as defined in the protocol. Any tumor assessments occurring after the start of a new anticancer treatment will be censored per the FDA censoring rules.

\*\* More than one consecutive missed visit/adequate tumor assessment is defined as the duration between two consecutive tumor assessments or the duration between the last adequate tumor assessment and death/PD is longer than (>) 97 days [= ((6+1) x 2 x 7) - 1] for subjects on every 6 weeks tumor assessment schedule in the first 18 weeks (6 cycles) of treatment; longer than (>) 139 days [= ((9+1) x 2 x 7) - 1] for subjects on every 9 weeks tumor assessment schedule from weeks 18 to 54 (Cycle 7 to Cycle 18); longer than (>) 195 days [= ((12+2) x 2 x 7) - 1] for subjects on every 12 weeks tumor assessment schedule after Week 54 in this study.

For subjects moving from one schedule to another:

Missed Week 18 and Week 27 assessments: (>)118 days [= ((6+1) + (9+1)) x 7 - 1]

Missed Week 54 and Week 66 assessments: (>)167 days [= ((9+1) + (12+2)) x 7 - 1]

If a subject had PFS event (#2, #5 or #6), the earliest event date will be used.

The priority of the censoring rules is described as follows:

- If a subject missed two or more consecutive tumor assessments before PD or death (#7), the subject will be censored at the date of the last adequate tumor assessment before the missed tumor assessments.

Note that if a subject is censored by both this criterion and start of new anticancer therapy criterion, the earliest censoring date will be used.

- If a subject did not have PD or death, the censoring date will be the earliest censoring date if the subject met multiple censoring criteria (#1, #3, #4, #7).

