### Sensitivity Analysis of PFS

Sensitivity analyses of PFS will be based on the Full Analysis Set using censoring rules from [Table 2](#), along with the following exceptions listed below:

Sensitivity Analysis 1: In this analysis, baseline tumor removal before or after completion of the Week 18 tumor assessment will be evaluated as part of the study drug therapy and will not be considered as a new anticancer therapy (see difference in [Table 2, rule 4](#)).

Sensitivity Analysis 2 ([EMA guidance \[Reference 11\]](#)): In this analysis, PD or death after two or more missing assessments, or after receiving a new anticancer therapy will be considered as a PFS event (see differences in [Table 2, rules 4 and 7](#)). The removal of baseline lesion(s) before or after completion of the Week 18 tumor assessment will be considered as a new anticancer therapy.

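### Table 2 rule 6 lacks the new-therapy condition that rules 2 and 5 carry, so a death soon after a switch or lesion removal is censored by rule 4 and an event by rule 6, with no ranking between them

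*SAP*

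**What the plan says.** Four places in SAP Section 6.4.1 bear on the point.

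- **Rule 4** censors a subject once new anticancer therapy starts, at the "Date of last adequate radiologic assessment on or prior to the start of new anticancer therapy". It makes no exception for a later death. The text before Table 2 brings lesion removal under this rule: "assessments after removal of baseline lesion(s) (considered as a new anticancer therapy) before or after Week 18 will be censored".
- **Rule 5** counts a death as an event only in this situation: "Death without disease progression or any new anticancer therapy". Rule 2 limits progression events in the same way.
- **Rule 6** counts as an event, at the date of death, "Death between adequate assessment* (Death before next scheduled assessment or after exactly one missing assessment"). It is silent on new therapy.
- **The priority text below Table 2** says: "If a subject had PFS event (#2, #5 or #6), the earliest event date will be used". It then gives two bullets. The first censors subjects with two or more consecutive missed assessments before progression or death (rule 7). Its note takes the earlier date if the new-therapy criterion also applies. The second begins: "If a subject did not have PD or death, the censoring date will be the earliest censoring date".

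Sensitivity Analysis 2 then states that "PD or death after two or more missing assessments, or after receiving a new anticancer therapy will be considered as a PFS event", and names rules 4 and 7 as the places where it departs from Table 2.

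**The concern.** Two rows of the table give the same subject different outcomes on the primary endpoint. Which one prevails would depend on the order in which the derivation program applies the rows.

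If rule 6 is applied as written, deaths shortly after a switch count in primary PFS, while progressions after the same switch do not. Those deaths would also count towards the approximately 38 IIR events that set the data cutoff. Sensitivity Analysis 2 would no longer differ from the primary analysis on them, and Sensitivity Analysis 1 would no longer differ on deaths soon after lesion removal.

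The trial is open-label (Section 4.2), so switching and lesion removal may differ between arms. If the choice is left until results are known, it becomes a post hoc choice on the primary endpoint.

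**Working it through.** **Step 1. Apply the rules to a death without IIR progression, on the 6-weekly schedule.** The double-asterisk footnote to Table 2 sets the limit for more than one missed assessment at (6+1) × 2 × 7 − 1 = 97 days.

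| New therapy or lesion removal before death | Days from last adequate scan to death | Rules met | Result |
|---|---|---|---|
| No | up to 97 | 5 event, 6 event | consistent |
| No | over 97 | 5 event, 7 censored | first priority bullet: censored |
| Yes | up to 97 | 4 censored, 6 event | conflict, no ranking |
| Yes | over 97 | 4 censored, 7 censored | note: earlier date |

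Only the third row is unresolved. The same overlap exists up to (9+1) × 2 × 7 − 1 = 139 days on the 9-weekly schedule and (12+2) × 2 × 7 − 1 = 195 days on the 12-weekly schedule. At the transitions it is (7+10) × 7 − 1 = 118 and (10+14) × 7 − 1 = 167 days.

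**Step 2. Look for a clause that settles the third row.**

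- The single-asterisk footnote attached to rule 6 says: "Any tumor assessments occurring after the start of a new anticancer treatment will be censored per the FDA censoring rules". A death is not a tumor assessment.
- The first priority bullet and its note need two or more missed assessments, which this subject does not have.
- The second bullet lists rule 4 but covers only subjects without progression or death.
- The event sentence lists rule 6 with no exception for rule 4. It chooses among event dates and does not rank events against censoring.

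So no clause ranks rule 4 against rule 6.

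**Step 3. Read the intent.** Rule 5 excludes the same death. Sensitivity Analysis 2 counts it as a departure from rule 4, which makes sense only if the primary analysis censors it. The endpoint definition (Sections 6.1.1 and 6.4.1: progression or death, whichever is first) points towards the event, but it is general and Table 2 is meant to refine it.

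**Step 4. Size.** First, the plan's own figure. Inputs from Section 5: hazard ratio 0.4 (3.5/8.75), one-sided alpha 0.025, power 80%; 1:1 allocation from Section 4.2. Schoenfeld: (1.960 + 0.842)² / (0.25 × (ln 0.4)²) = 7.849 / 0.2099 = 37.4, so 38 events. The plan's 38 is reproduced, and 38 events give 80.6% power.

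The SAP does not say how many deaths fall in the third row. If 1 to 5 of 38 events were recoded as censored, with the hazard ratio held at 0.4, Schoenfeld power would be 79.6%, 78.5%, 77.4%, 76.2% and 74.9%. Because the cutoff is event-driven, the choice of reading could move the cutoff date instead.

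That calculation ignores which arm the deaths fall in. A simulation addresses this: 81 subjects (the ITT number in Section 6.3.2), exponential PFS with medians 3.5 and 8.75 months, the SAP scan grid, cutoff at 38 events, and an unstratified log-rank test under each reading at the same cutoff. The switching rates without progression and the median survival of 6 to 12 months after a switch are assumptions. Results show the move from rule 4 prevailing to rule 6 prevailing.

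| Assumed switching per month | Effect of letting rule 6 prevail |
|---|---|
| 1% in both arms | 0.4 to 0.8 events added |
| 2% in both arms | 0.9 to 1.5 events added; power 77.0% to 77.1%, or 77.5% to 77.6% |
| 5% in both arms | power falls 1.4 to 2.8 points |
| Arm A 5%, Arm B 2%, 6-month survival after switch | power 75.8% to 68.3% |
| Arm B switches more | power rises 1 to 2 points |

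Over switching of 2% to 5% per month, the mean number of added events reached about 4.6, and significance changed in 2% to 8% of simulated trials. The simulated powers should be compared with each other, not with the 80.6% from the formula.

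**The case against.** The strongest reply is that the intended answer can be read from the SAP. Rule 4 has no exception for death, rule 5 excludes the same death, and Sensitivity Analysis 2 names rule 4 as the rule that keeps it out of the primary analysis. Letting rule 6 override all three would leave rule 5's condition without effect inside the rule 6 window. This stands as evidence of intent. It does not remove the contradiction, because rule 6 and the event sentence still say otherwise.

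Second, Section 4.2.2.2 ends tumor assessments after treatment when another anticancer therapy starts, so a switched subject may have no next scheduled assessment and rule 6 may not reach that subject. This narrows the problem but does not close it. Section 9.1 continues assessments after discontinuation without that stop, and the position after lesion removal is unclear.

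Third, the group is narrow. Section 4.2.2.1 requires IIR confirmation of progression before study treatment is discontinued, with a safety exception. Section 4.2.4 requires it for crossover before the Extension Phase, and that progression is already an event unless rule 7 censors it. This stands: the cases are mainly lesion removal, or new therapy begun without IIR-confirmed progression.

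A reader might infer a stronger point, that the priority text settles the conflict in favor of the event. The document does not support that. The event sentence only selects among event dates, the list is headed as a priority of censoring rules, and the note to the first bullet applies the new-therapy criterion to subjects who have progressed or died. On rule 4 against rule 6 the text is silent.

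**Conclusion.** Rule 6 is wrong as written: for a death after new therapy or lesion removal, without IIR progression and inside the missed-assessment window, it contradicts rules 4 and 5 and the stated contrast of Sensitivity Analysis 2. The intent to censor is clear enough that this is a drafting error, not a disputed choice of method. The sample size calculation is unaffected.

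The size is probably small and cannot be fixed from the SAP. Under the assumed rates it is about 0.4 to 5 events against 38. With low and equal switching, the change in power is negligible, and one or two events sit comfortably within a trigger stated as approximately 38. A loss of about 7 points needs Arm A to switch more than Arm B and short survival after the switch, so it should not be quoted as the expected effect. The contradiction itself does not depend on any of these figures. It should be fixed before the primary analysis.

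**What to change.** 1. In Table 2, limit rule 6 to deaths with no new anticancer therapy, including removal of baseline lesions, started before death. This matches rule 5.
2. In the priority text, add that rule 4 takes precedence over rules 5 and 6 when new therapy starts before progression or death.
3. Keep both sensitivity analyses. Sensitivity Analysis 1 retains its exception for lesion removal, and that exception should carry through to the amended rule 6. Sensitivity Analysis 2 remains the analysis that counts these deaths.

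The cost is two lines of SAP wording and one line in the derivation program, with no new data. The change should be dated before the primary analysis.
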